6.1 Full Analysis Set

6.1.1 Phase 1 Full Analysis Set

The Phase 1 Full Analysis Set (P1FAS) is defined as all subjects that are enrolled in phase 1 and receive at least 1 dose of AMG 510. All safety and efficacy analysis for Phase 1 except the DLT analysis and interim ORR analysis will be performed on the P1FAS.

6.1.2 Phase 2 Full Analysis Set

The phase 2 full analysis set (P2FAS) will consist of all subjects that are enrolled in phase 2 and receive at least 1 dose of AMG 510. The analysis of safety, PFS, and OS for Phase 2 will be performed on the P2FAS.

6.2 Safety Analysis Set

The integrated Safety Analysis Set is defined as all subjects that are enrolled in phase 1 and phase 2 and receive at least 1 dose of AMG 510.

6.3 Per Protocol Set(s)

Not applicable to this study

6.4 Health-related Quality-of-Life or Health Economics Analyses Set(s)

The analysis set for Health-related Quality of Life outcomes will be defined in a Supplemental Statistical Analysis Plan along with the planned analyses for these endpoints.

6.5 Pharmacokinetic/Pharmacodynamic Analyses Set(s)

The PK Analysis Set will contain all subjects who have received at least 1 dose of the investigational product and have at least 1 PK sample collected. These subjects will be evaluated for PK analysis unless the number of data points required for analysis is not enough, or significant protocol deviations have affected the data, or if key dosing or sampling information is missing. The PK Analysis Set will be used to conduct the analysis of PK data, unless otherwise specified.

6.6 Interim Analyses Set(s)

Interim analyses for specific endpoints will use P1FAS, P2FAS, or those defined in [Section 6.7](#).

6.7 Study-specific Analysis Sets

6.7.1 DLT Evaluable Set

The Dose Limiting Toxicity Analysis Set will contain DLT-evaluable subjects. The details of DLT evaluable subjects are given below:

Dose Cohort	Duration of DLT Window	DLT Evaluable Subject
Multiple subject cohorts	21 days from C1D1	Subject experienced a DLT or Subject does not experience a DLT and subject received at least 80% of the planned doses (ie, no more than 4 days without dosing) of investigational product within the first treatment cycle of 21 days.

C1D1 = Cycle 1 Day 1; DLT = Dose-Limiting Toxicity

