2.6.1.1 Dose Selection Rationale

The proposed AMG 510 doses are 180, 360, 720, and 960 mg administered once daily (QD) orally (PO); a twice daily (BID) PO dose may be explored as discussed in [Section 3.1.1.1.2](#). During dose exploration (part 1) and dose expansion (part 2), AMG 510 will be given QD (or BID) PO for a treatment cycle of 21 days in length that include 21 administrations of AMG 510. The planned dose level(s) for dose expansion (MTD/RP2D) will be determined based on data collected during dose exploration.

The proposed clinical starting dose of 180 mg administered QD PO is based on the current guidance for starting dose of anti-cancer small molecule drugs ([ICH S9](#)) using the methodology described by the Food and Drug Administration (FDA) for calculating the human equivalent dose (HED) on a body surface area basis ([FDA, 2005](#)). The rat severely toxic dose in 10% of animals (STD₁₀) and the dog highest non-severely toxic dose (HNSTD) were 200 mg/kg/day PO and 300 mg/kg/day PO, respectively, as noted in the 28-day repeat-dose GLP toxicology studies. The proposed starting dose was roughly the maximum recommended starting dose of 195 mg/day PO, which is based on the lower value of 1/10th the HED for the rat STD₁₀ (195 mg/day PO) and 1/6th the HED for the dog HNSTD (1622 mg/day PO). To estimate AMG 510 exposures in humans, AMG 510 human PK parameters were predicted using allometric scaling of PK parameters for clearance and volume obtained from nonclinical studies in mice, rats, monkeys, and dogs and absorption constant and oral bioavailability following oral tablet administration of AMG 510, the same tablet formulation to be used in this clinical study. At the starting dose of 180 mg administered QD PO, the predicted exposure margins of steady-state maximum plasma concentration (C_{max}) and area under the plasma concentration-time curve (AUC) exposures relative to the rat STD₁₀ are 62-fold and 20-fold, respectively. The predicted exposure margins of steady-state C_{max} and AUC exposures relative to the dog highest severely toxic dose (HNSTD) are estimated at 50-fold and 12-fold, respectively, at the starting dose administered orally once daily.

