3.3 Number of Subjects

Participants in this clinical investigation shall be referred to as “subjects”.

It is anticipated that up to 158 subjects will be enrolled in the phase 1 part of the study. No more than 92 subjects will be enrolled in part 1 (dose exploration) cohorts and up to 66 subjects will be enrolled in part 2 (dose expansion) cohorts.

During part 1 (dose exploration), a subject that is not DLT-evaluable will be replaced with another subject to the same dose level. A subject is DLT-evaluable if either of the following occurs:

- Subject experienced a DLT or
- Subject does not experience a DLT and subject received at least 80% of the planned doses of investigational product within the first treatment cycle (ie, 21 days)

Subjects will not be replaced after end of the DLT period.

In phase 2, it is anticipated that approximately **200 subjects (at least 105 subjects with NSCLC and 60 subjects with CRC)** will be enrolled. **Actual enrollment for each tumor type (NSCLC, CRC) will be based on DLRT recommendations and Amgen's internal decision.**

The rationale for the number of subjects is provided in [Section 10.2](#).

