6.1.1.1 Dosage, Administration, and Schedule

AMG 510 will be administered orally once **or twice daily [BID]**), depending on what **phase and/or cohort of the study that the subject is enrolled. No drug holidays are allowed.** The effects of overdose of AMG 510 are not known. AMG 510 will be dispensed at the research facility by a qualified staff member. Subjects are required to take AMG 510 at the research facility on clinic visit days as described in [Table 2](#). Subjects will take AMG 510 at home on non-clinic visit days. AMG 510 must be administered in the fasted state (no food or liquids, except water, 2 hours before to 1 hour after dosing). On PK days (eg, cycle 1 day 1, cycle 1 day 8, and cycle 2 day 1 for Phase 1), subjects should eat a standard meal at least 2 hours before dosing. Subjects may eat the standard meal at home before clinic visit or in clinic.

Subject should take the AMG 510 dose at approximately the same time(s) every day. The AMG 510 dose should also not be taken more than 2 hours earlier than the **scheduled** time. A dose of AMG 510 can be replaced in the event of vomiting if the vomiting occur within 15 minutes of the dosing, all tablets administered have been accounted for (eg, 4 tablets must be collected if 4 tablets were administered) and are intact by visual inspection (not broken, partially dissolved, chewed, or crushed).

Subjects who receive AMG 510 once daily, should skip the AMG 510 dose if 6 hours have passed from the scheduled time of dosing. If a subject is enrolled to a twice daily (BID) cohort, doses should be taken approximately every 12 hours. For BID dosing, a subject should skip the AMG 510 if 2 hours have passed from the scheduled time of dosing.

The planned dose, start date/time, stop date, quantity administered, unit, planned frequency, reason for dose change/withheld, package lot number of AMG 510 are to be recorded on each subject's CRF(s).

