6.1.1.2.1 DLT Definition

A DLT is defined as any adverse event meeting the criteria listed below occurring during the first treatment cycle of AMG 510 (day 1 through day 21) where relationship to AMG 510 cannot be ruled out.

The grading of adverse events will be based on the guidelines provided in the CTCAE version 5.0. A DLT is defined as any of the following events during the first treatment cycle and attributable to AMG 510:

- Hematological toxicity
 - Febrile neutropenia
 - Neutropenic infection
 - Grade 4 neutropenia
 - Grade ≥ 3 thrombocytopenia for > 7 days
 - Grade 3 thrombocytopenia with grade ≥ 2 bleeding
 - Grade 4 thrombocytopenia
 - Grade 4 anemia
- Non-hematological toxicity
 - Grade ≥ 4 vomiting or diarrhea
 - Grade 3 diarrhea or grade 3 vomiting lasting more than 3 days despite optimal medical support
 - Grade ≥ 3 nausea for 3 days or more despite optimal medical support
 - Any other grade ≥ 3 adverse event

DLT-evaluable is defined as completion of 80% of AMG 510 doses within the first treatment cycle (ie, 21 days). A subject who experience a DLT within the first cycle is DLT evaluable regardless of number of doses taken. If a subject is withdrawn from study for any reason other than a DLT prior to completion of the 21-day safety

observation period, a replacement subject will be assigned the same dose as the replaced subject.

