Also, for subjects who discontinued study treatment without confirmed disease progression or start of subsequent anticancer treatment, tumor assessments will continue during LTFU every 12 weeks (\pm 2 weeks) for up to 3 years after last subject enrolled or until confirmed disease progression, start of subsequent anticancer treatment, death, withdrawal of consent, loss to follow-up, or end of study.

Subjects who had confirmed disease progression or started subsequent anticancer treatment, will be followed via telephone every 12 weeks (\pm 2 weeks) for assessment of survival and documentation of anticancer treatment. Subjects will be followed for up to 3 years after last subject enrolled or until withdrawal of consent, loss to follow-up, or subject death, whichever occurs first.

Maximum Tolerated Dose (MTD):

A final estimate of the MTD will be made based on a Bayesian Logistic Regression Model (BLRM) utilizing all DLT-evaluable subjects from the dose exploration and dose expansion cohorts. Based on the BLRM, the MTD is defined as the dose with the highest probability of a DLT rate between the targeted toxicity (0.2, 0.33) interval while controlling the probability of excessive and unacceptable toxicity below 25%. The MTD will be estimated separately by dosing regimen if multiple regimens are evaluated.

Objective Response Rate (ORR):

Objective response rate is defined as the proportion of patients with a BOR of CR or PR.

Overall survival (OS):

Overall survival (OS) is defined as the time from the start of treatment until event of death due to any cause. Subjects still alive will be censored at the date last known to be alive. If the date last known to be alive is after the date that triggers the analysis (ie, the data cutoff date), the subject will be censored at the analysis trigger date.

Primary Completion:

Defined as the date when the last subject is assessed or receives an intervention for the final collection of data for the primary endpoint(s) of Phase 2, for the purposes of conducting the primary analysis, whether the study concluded as planned in the protocol or was terminated early.

Progression Free-Survival (PFS):

The PFS is defined as interval from the start of treatment to disease progression or death due to any cause (whichever comes first). The censoring rules for the progression-free survival analysis are detailed in [Table 1](#).

Table 1. Main PFS Definition

Situation	Date of Event or Censor	Outcome

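### The SAP's days-based gloss on the 80%-of-doses criterion for DLT evaluability holds only for once-daily dosing and conflicts with that criterion in the twice-daily Part 1b cohorts

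*Supplement*

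**What the plan says.** SAP Amendment 1, Section 6.7.1, defines the DLT Evaluable Set in a one-row table. The row is labelled "Multiple subject cohorts", has a window of 21 days from the first dose, and makes no distinction by regimen. A subject is evaluable after a DLT or, without one, if the subject "received at least 80% of the planned doses (ie, no more than 4 days without dosing) of investigational product" in the first cycle.

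The protocol (Amendment 3) has the percentage without the days. Section 3.3 asks that the "subject received at least 80% of the planned doses of investigational product within the first treatment cycle", and replaces subjects in Part 1 who do not qualify. Section 6.1.1.2.1 says "DLT-evaluable is defined as completion of 80% of AMG 510 doses within the first treatment cycle (ie, 21 days").

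The same SAP covers Part 1b, the twice-daily cohorts (Section 3.1). These may be opened with about 12 subjects in 2 cohorts of 3 to 6. Protocol Section 6.1.1.1 sets the schedule: "If a subject is enrolled to a twice daily (BID) cohort, doses should be taken approximately every 12 hours". Table 4 also describes twice-daily administration. Protocol Section 2.6.1.1, however, describes dosing as "QD (or BID) PO for a treatment cycle of 21 days in length that include 21 administrations of AMG 510".

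DLT-evaluable subjects feed the Bayesian logistic regression model. SAP Section 5, under the definition of the MTD, adds: "The MTD will be estimated separately by dosing regimen if multiple regimens are evaluated".

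**The concern.** The link between the percentage and the parenthesis is an assertion that they are equivalent. A programmer needs something countable, and the parenthesis is the only countable form of the rule that the SAP gives. It counts days on which nothing was taken. With two doses a day, a subject can lose many doses without ever having such a day.

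The stake is the DLT rate of the twice-daily regimen. DLT incidence is a primary endpoint for Parts 1a, 1b and 2a, and the MTD is estimated by regimen. A subject who took well under 80% of the doses and had no DLT would be counted as DLT-free at the nominal dose. If DLT risk rises with exposure, as the dose-toxicity model assumes, that dilutes the apparent toxicity, which is the unsafe direction. In a cohort of 3 to 6, one such subject is 1/3 to 1/6 of the data.

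Part-day misses are possible under the dosing rules. Protocol Section 6.1.1.1 says "For BID dosing, a subject should skip the AMG 510 if 2 hours have passed" from the scheduled time, against 6 hours for once-daily dosing. The documents give no adherence data, so how often this happens is unknown.

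The same parenthesis stands in the first SAP, which was written for a once-daily protocol. It appears to have been carried forward when the twice-daily cohorts were added.

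**Working it through.** **Inputs.** Cycle and DLT window: 21 days (SAP 6.7.1). Threshold: 80% of planned doses (SAP 6.7.1; protocol 3.3 and 6.1.1.2.1). Days allowed without dosing: 4 (SAP 6.7.1). Doses per day: 1 for once-daily; 2 for twice-daily, from the 12-hourly schedule in protocol 6.1.1.1. The figure of 42 planned doses is derived: 21 × 2.

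**Formulas.** Minimum doses = 0.80 × planned doses, rounded up. With 4 days empty, 17 days remain. Fewest doses compatible with the gloss = 17 × 1; most = 17 × doses per day.

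**Once-daily: the SAP's figure reproduces.** 0.80 × 21 = 16.8, so 17 doses, or at most 4 missed. Four empty days: 17/21 = 81.0%, which passes. Five empty days: 16/21 = 76.2%, which fails. The gloss is exact.

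**Twice-daily.** 0.80 × 42 = 33.6, so 34 doses, or at most 8 missed.

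| Pattern over 21 days | Days without dosing | Doses taken | Share of 42 | Passes days gloss | Passes 80% |
|---|---|---|---|---|---|
| Both doses on 17 days, none on 4 | 4 | 34 | 81.0% | yes | yes |
| Morning dose only, every day | 0 | 21 | 50.0% | yes | no |
| One dose on 17 days, none on 4 | 4 | 17 | 40.5% | yes | no |
| Both doses on 16 days, none on 5 | 5 | 32 | 76.2% | no | no |

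Four or fewer empty days is therefore necessary for 80% but not sufficient. At exactly 4 empty days, the gloss is compatible with anything from 17 to 34 doses, and it agrees with 80% only when both doses are taken on all 17 remaining days.

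**The denominator.** Protocol 2.6.1.1 gives 21 administrations per cycle in a sentence that covers both regimens. Twelve-hourly dosing gives 42. If the 21 were used as the planned number for a twice-daily subject, 17 doses would score 17/21 = 81% instead of 17/42 = 40.5%.

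**The case against.** The strongest reply is that the 80% requirement has not gone away. It stands first in the SAP sentence, and protocol Sections 3.3 and 6.1.1.2.1 state it with no days gloss. The SAP presents itself as detailing the protocol's analyses, and its list of changes (Section 10) names only PFS2. A reader might infer from the parenthesis that a twice-daily subject with 17 of 42 doses is DLT-evaluable under the plan. The documents do not support that: 17/42 fails the percentage, and protocol 3.3 would have the subject replaced. The subject is admitted only if the days count is applied in place of the percentage. This part of the reply stands. What it leaves open is that the SAP asserts an equivalence that is false for a regimen it covers, and does not say which half governs when they disagree.

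A reader might also infer a sizeable bias in the twice-daily DLT rate. The plan gives neither adherence data nor a relation between missed doses and DLT risk, so no such figure can be derived. Heavy under-dosing may also be rare. Suppose, purely as an assumption, that every morning dose is taken and each evening dose is skipped independently with probability 30%, 40% or 50%. Then 15%, 48% or 81% of subjects would take fewer than 34 doses, but those subjects would average about 77%, 75% or 73% of doses, just under the line. The 50% and 40% patterns in the table mark what the gloss permits and are not forecasts.

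Further, Part 1b is optional and small, and SAP Section 9.6.7 summarises number of doses and relative dose intensity, so gross under-dosing would be visible. Section 2.6.1.1 is background on dose selection, and nothing makes its count the denominator for evaluability. These points limit the reach of the problem but do not remove the conflict.

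**Conclusion.** The concern holds as an internal inconsistency. The days gloss in SAP 6.7.1 is exact for once-daily dosing and does not match the 80% criterion for the twice-daily cohorts, where it is met by subjects at 50% of planned doses and, at the extreme, 40%. If the gloss is what is programmed, under-dosed twice-daily subjects can be counted as DLT-evaluable and DLT-free, and the DLT rate for that regimen is biased downward in cohorts of 3 to 6. The direction follows if DLT risk increases with exposure; the amount cannot be calculated from the documents.

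The conclusion rests on 42 planned doses, which follows from the 12-hourly schedule in protocol 6.1.1.1. It affects only Part 1b, about 12 subjects if opened; once-daily cohorts are untouched. It should be corrected because it concerns a primary endpoint and the correction is easy.

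**What to change.** In SAP 6.7.1, either limit the parenthesis to once-daily cohorts, or replace it with the existing 80% criterion expressed in doses: at least 17 of 21 for once-daily and at least 34 of 42 for twice-daily dosing. This applies the protocol's own percentage and sets no new threshold. State that the percentage of planned doses governs.

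Separately, reconcile the administration count in protocol 2.6.1.1 with the twice-daily schedule in Section 6.1.1.1 and Table 4, so that the number of planned doses is unambiguous for each regimen.

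The cost is wording. Any additional replacements in Part 1b are those that protocol 3.3 already requires; their number depends on adherence and cannot be estimated from the documents.

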6.7.2 Phase 1 Monotherapy RP2D ORR Analysis Set

The phase 1 monotherapy RP2D ORR analysis set (P1OAS) will consist of all subjects with confirmed KRASp.G12C status whose initial dose of AMG 510 is at the RP2D and received at least 1 dose of AMG 510 in the phase 1 monotherapy dose exploration part, or the phase 1 monotherapy dose expansion part, and had at least 6-week response data. Subjects who stopped disease assessments prior to 6 weeks will be included in this analysis set if the data cutoff is at least 6 weeks after their first dose date. The futility and efficacy thresholds will be calculated for monitoring the antitumor activity of monotherapy of AMG 510 during phase 1 expansion part using this analysis dataset.

6.7.3 Phase 2 ORR Analysis Set

The phase 2 ORR analysis set (P2OAS) will consist of all subjects in the phase 2 full analysis set who have had at least 6 weeks response data starting from day 1. Subjects who stopped disease assessments prior to 6 weeks will be included in this analysis set if the data cutoff is at least 6 weeks after their first dose date. The interim futility analysis, primary analysis, and final analysis of ORR, DOR, and TTR will be performed on the P2OAS.

7. Planned Analyses

The following interim, primary, and final analyses for phase 1 and phase 2 portions of the study are planned.

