3.1.3 Phase 2 – AMG 510 Monotherapy

This is a multicenter, non-randomized, open-label, phase 2 study to evaluate efficacy and safety/tolerability of AMG 510 as monotherapy in subjects with *KRAS p.G12C* mutant advanced solid tumors (NSCLC, CRC, and other tumors). Approximately **200** subjects (**at least 105 for NSCLC and 60 CRC**) will be enrolled. **The timing to start enrollment into each tumor type will be communicated to the sites and may be gated based on Amgen's internal decision based on several factors (ie, efficacy and availability of the drug supply).** Tumor response will be evaluated employing

RECIST 1.1 criteria based on contrast enhanced CT/MRI imaging with assessments conducted by an independent radiological central laboratory. A combined efficacy analysis of all subjects enrolled to the confirmed monotherapy RP2D will be performed. Subgroup analysis of each tumor type will also be performed. Interim safety reviews will be conducted after 30, 50, 70, and 100 subjects have been enrolled and treated with AMG 510 in the phase 2 for at least 21 days (enrollment will not be held for completion of these safety reviews). Interim futility analysis will be conducted as described in [Section 10.4.1.3.2](#). The primary analysis for the study will occur **after there are at least 105 evaluable NSCLC subjects or 60 evaluable CRC subjects in the phase 2 ORR analysis set (Section 10.1.2.5)**, whichever occurs first. **The data cutoff will be decided to allow sufficient time to demonstrate durability of ORR.**

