7.5 Radiological Imaging Assessment

The extent of disease will be evaluated by contrast-enhanced MRI/CT according to **RECIST 1.1** ([Appendix D](#)). All radiological imaging will be performed as indicated in the Site Imaging Manual provided by the central imaging core laboratory. In order to reduce radiation exposure for subjects, low dose CT should be utilized whenever possible.

The screening scans must be performed within 28 days prior to enrollment and will be used as baseline. All subsequent scans will be performed in the same manner as at screening, with the same contrast, preferably on the same scanner. Radiological assessment must include MRI/CT of the chest, abdomen and pelvis, as well as assessment of all other known sites of disease as detailed within the Site Imaging Manual. Magnetic resonance imaging (MRI) of the brain should be performed if signs or symptoms suggestive of central nervous system metastases are present.

The same imaging modality, MRI field strength and intravenous and oral contrast agents should be used at screening should be used for all subsequent assessments. Liver specific MRI contrast agents should not be used. To reduce potential safety concerns,

macrocyclic gadolinium contrast agents are recommended per National Health Institute guidelines, or follow local standards if more rigorous.

During treatment and follow-up radiological imaging of the chest, abdomen, pelvis, as well as all other known sites of disease, will be performed independent of treatment cycle every 6 ± 1 weeks for the first 4 response assessments. After **four** 6-week response assessments, radiological imaging and tumor assessment will be performed every 12 ± 1 weeks. Radiologic imaging and tumor assessment will be performed until disease progression, start of new anticancer treatment, death, withdrawal of consent or until end of study. Imaging may also be performed more frequently if clinically necessitated at the discretion of the managing physician. Radiographic response (complete response, partial response) requires confirmation by a repeat, consecutive scan at least 4 weeks after the first documentation of response and may be delayed until the next scheduled scan to avoid unnecessary procedures.

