2.1.3 Phase 2 (AMG 510 Monotherapy)

Objectives	Endpoints
Primary	

 To evaluate tumor objective response rate (ORR), assessed by RECIST 1.1 criteria, of AMG 510 as monotherapy in subjects with KRAS p.G12C mutant advanced solid tumors (NSCLC, colorectal cancer [CRC], and other tumor types). 	
 Objective response rate (ORR = complete response [CR] + partial response [PR]), assessed per RECIST 1.1. Response will be assessed by independent radiologic review. Complete response and PR require confirmatory CT or MRI repeat assessment 4 weeks after the first detection of response.
Secondary	

 To evaluate other measures of AMG 510 efficacy as monotherapy in subjects with KRAS p.G12C mutant advanced solid tumors by RECIST 1.1 (NSCLC, CRC, and other tumor types). 
 Duration of response (DOR) Disease control rate (DCR) Time to response (TTR) Progression-free survival (PFS) Overall survival (OS) PFS rate at 6 months and 12 months OS rate at 12 months 	
 Duration of response - defined as time from first evidence of confirmed PR or CR to disease progression or death due to any cause, whichever occurs first. Subjects without a duration ending event will be censored at their last evaluable disease assessment date. Progression will be based on an independent radiologic assessment of disease response per RECIST 1.1 Disease control rate defined as CR + PR + stable disease rate measured as described for ORR Time to response - defined as time from first dose of AMG 510 until the first evidence of confirmed PR or CR Progression-free survival - defined as time from first dose of AMG 510 until disease progression or death from any cause, whichever occurs first. Subjects who do not progress or die will be censored at their last evaluable disease assessment date. Progression will be on an independent radiologic assessment of disease response per RECIST 1.1. Overall survival - defined as time from first dose of AMG 510 until death from any cause. Subjects who do not die will be censored at the date of last contact. Progression-free survival rate at 6 months and 12 months Overall survival rate at 12 months

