7.2 Primary Analysis

7.2.1 Phase 1

The primary analysis for phase 1 will occur when target enrollment in phase 1 dose escalation and dose expansion is complete and each subject either completes 6 months on study or withdraws from the study.

7.2.2 Phase 2

The primary analysis for phase 2 will occur after 105 NSCLC or 60 CRC subjects are enrolled in phase 2 and have 6-month follow-up, whichever group occurs first. The data cutoff was decided to allow sufficient time to demonstrate durability of ORR. Subjects who end the study prior to 6 months will be counted. The data will be analyzed once they have been entered, cleaned, and locked. The primary analysis will summarize for all tumor types even if it is triggered by 105 NSCLC subjects or 60 CRC subjects.

Results from the tumor cohort without sufficient subjects with 6-month follow up will be used descriptively. A subsequent analysis when the prespecified number of subjects in this cohort reach 6 months follow-up is outlined in [Section 7.3.2](#).

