9.7.4 Analyses of Biomarker Endpoints

Relationships between changes in tumor dynamics and above biomarkers of interest listed as exploratory endpoints will be explored. Changes in expression levels of biomarkers and their relationship to dose may also be explored. Summary statistics over time will be provided and graphical presentations may be used.

The relationship between AMG 510 exposure and related biomarkers in blood will be also explored if deemed appropriate. As appropriate, details of analysis will be provided in a supplemental analysis plan for exploratory biomarker analysis.

10. Changes From Protocol-specified Analyses

PFS2 is added as exploratory endpoint analyses.

11. Literature Citations / References

Kalbfleisch, J. D. and Prentice, R. L. *The Statistical Analysis of Failure Time Data*, New York: John Wiley & Sons; 1980

Klein, J. P. and Moeschberger, M. L. *Survival Analysis: Techniques for Censored and Truncated Data*, New York: Springer-Verlag; 1997.

Clopper C.J. and Pearson E.S. The Use of Confidence or Fiducial Limits Illustrated in the Case of the Binomial. *Biometrika* Vol. 26, No. 4 (Dec., 1934): 404-413

12. Prioritization of Analyses

No priority of output is planned for this study.

13. Data Not Covered by This Plan

The analysis of Biomarkers and PRO endpoints is not covered in this plan.

14. Appendices

Appendix A. Technical Detail and Supplemental Information Regarding Statistical Procedures and Programs

Imputation Rules for Partial or Missing Stop Dates

If the month and year are present, impute the last day of the month. If only the year is present, impute December 31 of that year. If the stop date is entirely missing, assume the event or medication is ongoing. If a partial or complete stop date is present and the 'ongoing' or 'continuing' box is checked, then it will be assumed that the AE or con-med stopped and the stop date will be imputed, if partial.

Imputation Rules for Partial or Missing Start Date:

Start Date		Stop Date						Missing
		Complete: yyyyymmdd		Partial: yyyyymm		Partial: yyyy		

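### The phase 2 ORR set admits subjects at 6 weeks, before a response can be confirmed, and the protocol and SAP trigger the primary analysis differently; under the SAP the effect is conservative and small

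*Supplement*

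**What the plan says.** The versions read are protocol Amendment 3 (22 May 2019) and SAP Amendment 1 (16 July 2019).

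- **Analysis set.** SAP 6.7.3 defines P2OAS as "all subjects in the phase 2 full analysis set who have had at least 6 weeks response data starting from day 1". A subject who stopped assessments earlier "will be included in this analysis set if the data cutoff is at least 6 weeks after their first dose date". Protocol 10.1.2.5 has the same definition. The set serves the interim futility looks and the primary and final analyses of ORR; the SAP adds DOR and TTR.
- **Endpoint.** SAP 2.1.3: "Complete response and PR require confirmatory CT or MRI repeat assessment 4 weeks after the first detection of response". Under the SAP's definition of best overall response, an unconfirmed PR is not a response.
- **Scans.** Protocol 7.5 schedules imaging "every 6 ± 1 weeks for the first 4 response assessments" and says the confirmatory scan "may be delayed until the next scheduled scan to avoid unnecessary procedures".
- **Protocol trigger.** Protocol 3.1.3 places the primary analysis "after there are at least 105 evaluable NSCLC subjects or 60 evaluable CRC subjects in the phase 2 ORR analysis set", whichever comes first; 10.4.2 agrees. Both add that the cutoff will be chosen so that durability can be shown, without a minimum time. Protocol 10.4.3, for the second cohort, uses the same evaluability trigger without that clause.
- **SAP trigger.** SAP 7.2.2 places the primary analysis "after 105 NSCLC or 60 CRC subjects are enrolled in phase 2 and have 6-month follow-up, whichever group occurs first". It counts subjects who leave the study earlier and treats the other cohort as descriptive until its own 6-month analysis (7.3.2).
- **Recorded changes.** SAP section 10 lists one item only: "PFS2 is added as exploratory endpoint analyses".

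**The concern.** A 6-week rule suits the futility looks. For a confirmed-response endpoint it is too short: a subject with a week-6 partial response and no second scan yet sits in the denominator and counts as a non-responder. That lowers the observed ORR and the lower confidence limit compared with the 23% (NSCLC) or 10% (CRC) benchmark.

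The trigger matters because it decides how many such subjects there are. The protocol counts subjects evaluable in the 6-week set, and the SAP counts subjects with 6 months of follow-up. A reader of SAP section 10 would not learn that the trigger had changed. For the second cohort, protocol 10.4.3 and SAP 7.3.2 differ with no durability clause to bridge them.

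**Working it through.** **Time to confirmation.** The first scan falls at week 5 to 7. Adding 4 weeks gives week 9 to 11. If confirmation waits for the next scheduled scan, it falls at 12 ± 1, that is week 11 to 13. Entry at 6 weeks is therefore at least 3 weeks too early.

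**The plan's own figures (protocol 10.2.2).** Find the smallest count x whose two-sided 95% Clopper-Pearson lower limit, the 0.025 quantile of Beta(x, n − x + 1), exceeds the benchmark.

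- NSCLC, n = 105, 23%: 34/105 = 32.4%, lower limit 23.6%; 33/105 gives 22.7% and fails.
- CRC, n = 60, 10%: 12/60 = 20.0%, lower limit 10.8%; 11/60 gives 9.5% and fails.

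The stated minimum ORRs of 32% and 20% reproduce. The true ORRs behind the stated 90% probability are not given. Solving P(X ≥ 34 | 105, p) = 0.90 and P(X ≥ 12 | 60, p) = 0.90 gives about 37.9% and 26.4%. The calculations below use 38% (power 90.2%) and 26.4% (90.1%).

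**SAP trigger with continued enrolment.** Assume NSCLC enrolment continues at r per month after the 105th subject and the cutoff is 26 weeks after that subject's first dose. Extra subjects with at least 12 weeks of data enrolled in the first 26 − 12 = 14 weeks. Those with 6 to 12 weeks enrolled in the next 6. With 52/12 = 4.33 weeks per month, and every immature subject counted as a non-responder (an upper bound):

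| r per month | mature extras | immature extras | N | needed | power |
|---|---|---|---|---|---|
| none | 0 | 0 | 105 | 34 | 90.2% |
| 5 | 14 × 5/4.33 ≈ 16 | 6 × 5/4.33 ≈ 7 | 128 | 40 | P(X ≥ 40 given 121, 0.38) = 88.8% |
| 10 | 14 × 10/4.33 ≈ 32 | 6 × 10/4.33 ≈ 14 | 151 | 46 | P(X ≥ 46 given 137, 0.38) = 87.6% |

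The loss is 1.4 and 2.6 points. The second row needs 46 extra NSCLC subjects, while a total of about 200 leaves 200 − 105 − 60 = 35 places for all further enrolment. The same arithmetic for CRC at 5 per month gives N = 60 + 16 + 7 = 83, 15 needed, and P(X ≥ 15 given 76, 0.264) = 93.0%, so no loss against the planned 60.

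**Worst cases, for scale.**

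- Cutoff at the moment the protocol's count is reached, with m subjects not yet confirmable. NSCLC, P(X ≥ 34 given 105 − m, 0.38): 78% at m = 7 and 59% at m = 14. CRC, P(X ≥ 12 given 53, 0.264): 78% at m = 7.
- SAP trigger with every extra subject immature. 40/105 has a lower limit of 28.8%; 40/115, 40/125 and 40/135 give 26.1%, 23.9% and 22.1%. Only the last falls below 23%.

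**The case against.** The strongest reply is that the SAP has already settled the matter. The protocol deferred the cutoff until durability could be shown, and the later SAP fixes it at 6 months with nearly the same justification. Six months is well past confirmation, so the subjects who trigger the analysis are mature, or left early and are ordinary non-responders. The non-triggering cohort is descriptive until its own analysis, and other tumour types have no benchmark. Any remaining bias makes success harder, so it cannot produce a false claim.

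Most of this stands. It defeats two stronger readings that a reader might infer. One is that unconfirmable subjects necessarily dilute the benchmark ORR, with power falling to 78% or 59%. That requires a cutoff at 6 weeks, which the durability clause in protocol 3.1.3 and 10.4.2 argues against. The other is the overshoot to 40/135. It needs 30 subjects enrolled in the 6-week window and none in the preceding 14 weeks, or about 30 × 4.33/6 ≈ 22 per month starting from zero.

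Three things survive. Nothing in SAP 6.7.3 confines P2OAS to subjects meeting the 6-month criterion, and the targets are minimums. The durability clause sets no minimum time and is missing from protocol 10.4.3. Section 10 of the SAP is silent on the trigger.

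**Conclusion.** The concern holds in limited form. The entry rule is shorter than the endpoint's observation time, and the two documents state different triggers with the change unrecorded.

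Under the SAP, dilution is confined to subjects enrolled beyond 105 NSCLC or 60 CRC and to the descriptive pooled ORR. It is downward, leaves type I error uninflated, and costs about 1 to 3 points of NSCLC power relative to the planned 105. That size rests on assumptions not in the documents: accrual of 5 to 10 per month, true ORRs solved back from the stated 90%, and every immature subject counted as a non-responder.

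It would be tempting to say that the documents set cutoffs 26 − 6 = 20 weeks apart. They do not, because the protocol fixes no cutoff date for the primary analysis. Severity is minor to moderate.

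**What to change.** 1. In SAP 6.7.3 and protocol 10.1.2.5, for the primary and subsequent-cohort analyses, define P2OAS by tumour type as treated subjects whose first dose was at least 6 months before the data cutoff, whatever their assessments. Early dropouts then stay in as non-responders.
2. Keep the 6-week set for the interim futility looks only.
3. Align protocol 3.1.3, 10.4.2 and 10.4.3 with the SAP's 6-month trigger, replacing the open-ended cutoff wording.
4. List the trigger and the set definition in SAP section 10.

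This changes wording only and needs no new data. The cost is that late-enrolled subjects are reported in a later analysis. It should be settled before primary efficacy data are reviewed.
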